Judgment criteria	
The main judgment criterion for the HR will be the evaluation of the concordance between the measurements obtained following the application of the reference technical processes of non-operator dependent measurement taking via a CE marked device and via COBOX.
 
The secondary judgment criterion associated with the measurement of the RR will also be the subject of an evaluation of the concordance between the measurements obtained via a reference method of manual counting

	
according to the good practices of the medical or paramedical nursing staff (or arc or tec) and via COBOX.
 
For each of the parameters measured, we will establish the repeatability of the measurement and its accuracy (comparison of the relative error expressed as a percentage between the two types of measurement).

Study size	323 patients
Planned number of centers	4
Search duration	
Duration of participation for each patient: less than 30 minutes
 
Total research duration: 3 months
 
Approximate study start date: mid-July 2022
 
Approximate study end date: mid-October 2022

Statistical analysis of data	
The performance of the tool will be estimated by the concordance between the measurements obtained from the application of the reference technical process via a CE marked device and with the measurements obtained by COBOX.
 
An intraclass correlation coefficient (ICC) with its 95% confidence interval (95% CI) will be calculated. Measurement errors will be calculated and expressed as a percentage (root mean square error, etc.).
 
The two study samples will be compared by Student's t test and Fischer's F, with a desired significance for P value = 0.05, for all the analyses.
 
A DIXON test will be performed to assess the presence of statistically outliers within the samples.

Expected benefits	
These data will enable the COBOX tool, a class IIA medical device, to be validated in terms of measurement performance compared to a CE-marked device used in a reference technical process for taking measurements and a reference method for manual counting. Applications for taking constants without contact have a wide field of application in

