- Establish and verify the clinical safety of COBOX and detect any adverse side effects under normal conditions of use of the device and assess whether these constitute an acceptable risk in relation to the expected benefits of the device concerned.
- Evaluate ergonomics and user feedback.
- Evaluate the ease of use of the device (assessed by an ad-hoc questionnaire completed by the caregivers (or arc or tec), one questionnaire per caregiver and per type of device).

Justification of methodological choices

We are carrying out an observational, multicenter, prospective clinical investigation, evaluating the performance of the COBOX device in the context of and within the framework of usual care. Heart rate and respiratory rate are two physiological parameters measured when a patient arrives at the emergency room, so, given the high attendance of these services, it seemed to us to be an excellent place for this study. This measurement is carried out as part of the patient's care pathway using reference technical processes for taking measurements via a CE marked device and a reference method of manual counting. The inclusions of patients consulting in the emergency department make it possible to quickly obtain both a large number of inclusions, and on the other hand, a great variability of the constants noted due to the various pathological states. This approach allows great reproducibility in all clinical situations and thus makes it possible to validate performance in different contexts. In addition, a medico-economic study of the tool will be carried out.

Hypotheses

- H_0 :Routine care measurements in French care services, taken by the COBOX solution are different from measurements obtained through the application of reference technical processes and a manual counting reference method.
- H_1 :The current care measurements in French care services taken by the COBOX solution are consistent with the measurements obtained via the application of the reference technical processes and a reference method of manual counting.

Claims and expected performance of the investigational device that need to be verified.

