10. STATISTICAL ASPECTS

Study size calculation

Considering the results of the performance verification tests of the medical device under study, we have established the study hypotheses in connection with the calculation of the size of the study set out below:

Minimum acceptable value of the ICC correlation coefficient (ρ_0)	0.6
Expected value of the ICC correlation coefficient (ρ_1)	0.7
The number of observations per subject k	3
Two-sided significance level (α)	0.05
Power (1 - β):	90%
Minimum size (n)	226
Size at 30% safety margin	323

A final study size of 323 patients is retained; taking into account a rate of unusable data of 30% in order to maintain the statistical power of the study in the event of exclusion of outliers.

Statistical methods used

The analysis will carry an initial descriptive part. The qualitative variables will be expressed in frequencies (with their 95% CI), and the quantitative variables expressed in means (with their standard deviation) if the distribution is normal. Otherwise, the quantitative variables will be expressed as the median (with their interquartile range).

Then, we will perform a comparative analysis, using chi 2 tests (or Fisher's exact) for the qualitative variables and student test (or Mann-Whitney test if applicable) for the quantitative variables. For performance estimation, we will determine the intra-class correlation coefficient with its confidence interval and we will perform a graphical analysis of Bland and Altman. In addition, we will calculate the mean square errors between the measurement with COBOX and the reference measurements, and they will be expressed as a percentage.

All our analyzes will be carried out at the 5% significance level.

An analysis of the repeated and compared measurements between COBOX and the CE marked device (used during the technical reference process for taking measurements) for the heart rate will make it possible to evaluate the reproducibility of the COBOX on repeated measurements in the *COBOX Protocol Valid*

same individual. A secondary statistical analysis will be done for the measurement times T+5s and T+10s.

We will use imputation methods or sensitivity analysis for the management of missing data.

11. Access rights to source data and documents

Access to data

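### Read naturally, the plan's Dixon test screens each method's readings for extreme patients, although a device error in a concordance study shows in the paired difference; as a single-outlier test it is also masked by several errors

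*Combined protocol and SAP*

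**What the plan says.** - **Section 1, Research Summary, statistical analysis row.** "The two study samples will be compared by Student's t test and Fischer's F", and directly afterwards "A DIXON test will be performed to assess the presence of statistically outliers within the samples". The row does not say whether the values are readings or differences, whether the unit is a patient or a single reading, which Dixon ratio is used, or how many outliers are tested for.
- **Section 10, Study size calculation.** The Dixon test is not mentioned, but removal of outliers is foreseen: 323 patients are taken so as to "maintain the statistical power of the study in the event of exclusion of outliers". No rule says which values may be removed.
- **Section 10, Statistical methods used.** "All our analyzes will be carried out at the 5% significance level". The section also plans a Bland-Altman plot and mean square errors, neither of which is named as the outlier rule.
- **Section 5, Justification of methodological choices.** The emergency department was chosen partly because it supplies "a great variability of the constants noted due to the various pathological states".
- **Section 6, Primary endpoint.** The endpoint is the ICC between COBOX and the reference for heart rate, with three paired readings per patient.

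**The concern.** Disagreement between two methods is a property of the pair. A patient at 170 bpm on both devices is extreme in each sample but shows perfect agreement. A patient at 80 bpm whom COBOX reads as 120 is unremarkable in the COBOX sample but has a 40 bpm error. A within-sample test therefore looks first at the patients the setting was chosen to provide, and passes over an error that stays in the usual range.

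The classical Dixon ratio also looks for one suspect value. Two similar errors on the same side close the gap that it measures.

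Because Section 10 foresees removing outliers without a rule, true extremes could be dropped while in-range device errors stay in.

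**Working it through.** **Inputs from the documents.** n = 323; three readings per patient, so 323 × 3 = 969 pairs; 5% level; expected COBOX-reference SD for heart rate 5 bpm (Section 5, claims and expected performance).

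**Assumptions.** The documents give no heart-rate distribution. Mean 85 bpm, SD 18 (range 15 to 22), normal or lognormal, and error SD 4 to 5 bpm are assumed.

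**The plan's own figure.** C0 = (1 + 3 × 0.6/0.4)/(1 + 3 × 0.7/0.3) = 5.5/8 = 0.6875. Then n = 1 + 2(1.960 + 1.282)² × 3/[(ln 0.6875)² × 2] = 225.5, rounded up to 226, and 226/0.70 = 322.9, rounded up to 323. The sample size reproduces. No figure is stated for the Dixon test.

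**The statistic.** The basic ratio is r10 = (gap between the extreme value and its neighbour)/(range). At n = 323 its simulated 5% critical value under normality is about 0.145 for the upper tail and 0.170 for both tails. The r22 variant (0.218, both tails) skips one neighbour.

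**Hand illustration.** Take the other values to span about ±3 SD. Raw readings then run from 31 to 139 bpm (SD 18), and differences from −15 to +15 bpm (SD 5). Compare each ratio with 0.170.

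| Case | Ratio | Flagged? |
|---|---|---|
| Raw: true 150 | (150 − 139)/(150 − 31) = 0.09 | no |
| Raw: true 170 | (170 − 139)/(170 − 31) = 0.22 | yes |
| Raw: 80 read as 120 | 120 is below 139 and does not enter the ratio | no |
| Raw: 85 read as 185 | (185 − 139)/(185 − 31) = 0.30 | yes |
| Differences: one error, +40 | (40 − 15)/(40 + 15) = 0.45 | yes |
| Differences: errors of +38 and +42 | (42 − 38)/(42 + 15) = 0.07 | no |

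**Simulation, raw readings, one per patient.**
- No device error, lognormal, SD 15 to 22: a flag in about 15 to 23% of data sets (upper tail) or 10 to 17% (both tails). Normal heart rate: about 5%.
- All 969 readings pooled: under 1%, because a patient's three similar readings mask one another.
- Genuine tachycardia (normal, SD 18, r10/r22): 150 bpm flagged in 15%/17% of runs, 170 bpm in 91%/98%. At SD 15, 150 bpm is flagged in 74%/85%.
- One COBOX error of +40 bpm: it is the flagged top reading in about 2% of runs (lognormal, SD 18). Rerunning with SD 22 and SD 15 gives about 1% and 6% for lognormal heart rates, and 2% and 12% for normal ones.
- A true 60 read as 120: never the flagged value.
- Very large single errors (normal, SD 18, r10/r22): +80 bpm flagged in 57%/61%, +100 bpm in 88%/91% (lognormal, +100: 63%/75%).

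**Simulation, paired differences, errors of +40 bpm.**
- r10, upper tail, error SD 4 to 5: one error found in about 100% of runs, two in 15 to 22%, three in 6 to 11%.
- r22, both tails, SD 5: two errors still flagged in 100%, but three in 17% and five in 2%.
- Generalised ESD, up to 20 outliers, SD 5: about 98 to 99% of 30 bpm errors and about 100% of 40 to 60 bpm errors caught, with 1, 3, 5 or 10 present, and about 0.03 to 0.07 false flags per data set.

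**The case against.** The strongest reply is that the plan never says raw readings. That stands: the scale and unit are inferred from the neighbouring sentence. But nothing in the documents applies the test to differences, and if differences were meant, masking would remain.

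Two further points limit the concern:
- **Paired errors are not hidden.** A reader might infer that gross errors would go unseen in the report. The documents do not support that: the Bland-Altman plot and the error measures in Sections 1 and 10 use the pairs and would show them. They are not the outlier rule, however.
- **The effect on the ICC is small.** With SD 18, error SD 4 gives an ICC of 324/(324 + 16/2) = 0.976, and error SD 14 gives 324/(324 + 196/2) = 0.77. Deleting the flagged top reading changed the ICC by about −0.002 and −0.012 on average.

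It is also fair to say that raw values deserve some check, because staff type in the breath count (Section 8, Summary of patient follow-up).

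**Conclusion.** The point holds in limited form. As most naturally read, the named test has the wrong target for a concordance study, and as a single-outlier test it fails when several errors occur: from two with r10, from three with r22.

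Two stronger readings are not supported. One is that the test cannot see a COBOX error at all: single errors of roughly +80 to +100 bpm are often flagged. The other is that it generally flags tachycardia: this needs an isolated extreme and one value per patient, and it disappears when the three readings are pooled.

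The percentages rest on assumed heart-rate distributions, and respiratory rate was not simulated. That errors inside the patients' range are missed on raw readings and show on differences does not depend on those assumptions. The practical harm comes through the undefined removal of outliers. For a single flagged value it is small, but the outlier result would say little about COBOX.

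**What to change.** In the Research Summary, and matched in Section 10:

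1. Replace the Dixon test within the samples by a multiple-outlier screen of the COBOX-minus-reference differences, such as generalised ESD with a stated maximum number of outliers. State whether the unit is the patient or the single reading.
2. Use the screen only to list cases for technical review.
3. Keep all valid pairs in the primary ICC, and show any exclusion only as a sensitivity analysis.
4. Allow checks of raw values for entry errors, but do not exclude a value for being statistically extreme.

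The cost is a few sentences and a few lines of code. The downside is that gross device errors stay in the primary result, so the ICC may look slightly less favourable.

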COBOX is a tool for measuring cardiac and respiratory rhythm in routine clinical practice for patients outside intensive care and outside continuous monitoring. We expect a correlation coefficient of more than 0.7 between the COBOX measurements and those obtained using the reference method. Regarding the secondary endpoints, we expect average standard deviations

between COBOX and the reference methods of 5 bpm for the heart rate and 3 bpm for the respiratory rate.

Expected benefits

These data will validate the COBOX tool in terms of measurement performance compared to the results obtained through the application of reference processes for taking measurements using CE marked devices, as well as those obtained using the reference method of counting manual. Applications for taking physiological constants without contact have a wide field of application in the field of routine care and save medical time, increase quality by limiting manual copying errors and the risk of contamination.

6. Research design

Research scheme

This is an observational study, responding to Article 62.1 of the European medical device regulations, prospective, comparative.

Primary endpoint

The main judgment criterion will be the intra-class correlation coefficient between the measurement by COBOX and the measurement obtained thanks to the application of the reference processes for taking measurements via a measurement by a CE marked tool (for HR).

In order to ensure the repeatability of the device, three successive comparative measurements (each spaced 5 seconds apart) on the same patient will be carried out.

Secondary endpoints

The additional secondary judgment criteria will be:

- For RF (ranked criterion): comparison with a manual measurement following a reference method of manual counting according to good training practices for healthcare personnel trained in taking measurements (ide, as, internal external).
- The reliability of the reproducibility of the measurement
- The time in seconds dedicated to taking the parameters with and without the COBOX tool (time for installing and removing the tool if applicable, time for completing the medical file if applicable, effective time for taking the HR constants and FR).
- Assessment of treatment costs:
 - Pick-up times / delays
 - Total treatment costs (direct medical and non-medical costs)

Inclusion criteria

- Adult patient (18 years and over)
AND
- Patient consulting in the emergency department of a participating center
AND

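### The 90% power is calculated for three observations per subject, while the primary heart-rate ICC appears to rest on one COBOX–reference pair per patient; the 0.6 pass bar is implied but not stated

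*Combined protocol and SAP*

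**What the plan says.** All references are to the combined protocol and SAP.

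- **Section 6, Primary endpoint:** "The main judgment criterion will be the intra-class correlation coefficient between the measurement by COBOX and the measurement obtained" with a CE-marked tool, for heart rate. No value is attached. The same paragraph adds three successive readings per patient, for the purpose of repeatability.
- **Section 7:** the comparison is between COBOX and the Contec CMS60D.
- **Section 8, Summary of patient follow-up:** paired readings are taken at 15, 20 and 25 seconds.
- **Section 10, Study size calculation:** "Minimum acceptable value of the ICC correlation coefficient" is 0.6, the expected value is 0.7, and "The number of observations per subject k" is 3. With two-sided 0.05 and 90% power the minimum is 226, raised to 323 for 30% unusable data.
- **Section 10, Statistical methods used:** "we will determine the intra-class correlation coefficient with its confidence interval and we will perform a graphical analysis". On the later readings: "A secondary statistical analysis will be done for the measurement times T+5s and T+10s".
- **Section 5:** H1 says that measurements "taken by the COBOX solution are consistent with the measurements obtained via the application of the reference technical processes", without an ICC value. Under the heading "Claims and expected performance of the investigational device that need to be verified" stands the sentence "We expect a correlation coefficient of more than 0.7 between the COBOX measurements and those obtained using the reference method".

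**The concern.** The sizing formula takes k as the number of interchangeable measurements that enter the ICC for each subject. An ICC between COBOX and the oximeter at one time point has two. Three is the number of repeat readings, which section 6 introduces for repeatability and of which section 10 makes the second and third secondary. If the primary ICC uses the first pair only, the stated power belongs to a different analysis.

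The pass rule is a second, smaller gap. The objective is to validate heart-rate performance, but no analysis paragraph says what the ICC or its confidence limit must exceed. The 0.6 is found only in the sizing table, and a second figure, 0.7, stands under a heading about claims to be verified. The form of the ICC (absolute agreement or consistency) is not named either. Section 15 has the sponsor analyse its own device, which is a further reason to fix rule, form and reading in writing beforehand.

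**Working it through.** **Inputs (section 10):** ρ0 = 0.6, ρ1 = 0.7, two-sided α = 0.05, power 90%, k = 3, unusable 30%.

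**1. Reproduce the plan's figure.** The usual ICC sample-size formula is

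n = 1 + 2k(z₀.₉₇₅ + z₀.₉₀)² / [(k − 1)(ln C)²], with C = [1 + kρ0/(1 − ρ0)] / [1 + kρ1/(1 − ρ1)].

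Here (1.960 + 1.282)² = 10.507. For k = 3:

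- C = (1 + 3 × 1.5)/(1 + 3 × 2.333) = 5.5/8 = 0.6875; (ln C)² = 0.1404
- n = 1 + 6 × 10.507/(2 × 0.1404) = 225.5, so 226
- 226/0.7 = 322.9, so 323

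Both figures match exactly. The exact F calculation (one-way ICC, degrees of freedom n − 1 and n(k − 1), 0.025 per side) gives 90.2% power at n = 226.

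**2. Same inputs with one pair per patient (k = 2).**

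- C = (1 + 2 × 1.5)/(1 + 2 × 2.333) = 4/5.667 = 0.7059; (ln C)² = 0.1213
- n = 1 + 4 × 10.507/0.1213 = 347.4, so 348
- 348/0.7 = 497.1, so 498 enrolled at 30% unusable

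Exact power for a lower 95% limit above 0.6 at a true ICC of 0.7:

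| Usable patients | k = 3 | k = 2 |
|---|---|---|
| 226 | 90.2% | 74.2% |
| 323 (none unusable) | 97.3% | 87.8% |

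**3. Dependence on ICC form and bias.** Simulation of the two-way absolute-agreement ICC with its F-based interval (one pair, 4,000 studies per case, true ICC held at 0.70). Bias is a constant device difference in units of the total heart-rate SD. It is an assumption, since the documents give neither a bias nor a heart-rate SD.

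| Bias | n = 226 | n = 323 | n = 348 |
|---|---|---|---|
| none | 73% | 88% | 90% |
| 0.2 SD | about 61% | about 75% | about 77% |
| 0.32 SD | about 20% | about 20% | about 20% |

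Without bias this agrees with step 2. With bias the power is lower, and extra patients recover little of it.

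**4. Size of the pass-rule gap.** Exact F, one-way ICC, k = 3, n = 226:

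| True ICC | Lower limit > 0.6 | Point estimate > 0.7 |
|---|---|---|
| 0.70 | 90.2% | 49.5% |
| 0.75 | 99.9% | 97.1% |
| 0.80 | 100% | 100% |

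The two rules differ materially only if the true ICC is close to the planning value.

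**The case against.** **On the pass rule.** A value called the minimum acceptable, a two-sided 5% sizing test and a 95% confidence interval together point to one rule: lower limit above 0.6. The 0.7 sentence begins with an expectation, and the sizing table uses the same word for 0.7, so it is most naturally the planning value. This largely stands. What remains is that the rule has to be inferred, and that the heading over the 0.7 sentence speaks of claims to be verified.

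A reader might go further and infer that no bar exists, or that the device must show a lower limit above 0.7, which a true ICC of 0.70 would meet only 2.5% of the time. No passage states that second rule, so disagreement rates built on it do not measure a defect in this plan.

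**On the sample size.** A reader might infer that 226 is miscalculated. It is not: it follows exactly from the listed inputs. The question is whether k = 3 describes the primary analysis. Section 6 does mention three comparative readings under the primary endpoint, so an analysis using all three pairs is possible. That would be two methods by three readings, six values per patient in a crossed layout, and the k = 3 formula does not describe it either. Its power depends on how far the COBOX–oximeter difference repeats between readings 5 seconds apart, which the documents do not give.

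**On bias.** A reader might take the 5 bpm in section 5 as a constant device bias and work out a loss in the ICC. Section 5 gives 5 bpm as a standard deviation, and no heart-rate SD is documented, so such a sum is only illustrative.

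**Conclusion.** The concern holds in two parts.

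The main part is the mismatch between sizing and endpoint. If the primary ICC uses one COBOX–reference pair per patient, as the two-method endpoint and the secondary status of the later readings suggest, the stated 90% power does not apply. It is about 74% at the 226 usable patients that the plan expects, and 88% only if none of the 323 is lost; 90% would need 348 usable. This rests on a true ICC of 0.7, a test against 0.6, and a one-way ICC or an absolute-agreement ICC with negligible bias. The one-pair reading is itself an inference, because the plan does not say in words which reading is primary.

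The lesser part is missing detail: the 0.6 bar is implied but not written as a decision rule, 0.7 is not labelled as a planning value, and the ICC form is not named. It could change the conclusion if the true ICC is near 0.70 and hardly matters from 0.75 upwards.

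Neither part makes the study unanalysable, and neither by itself requires a larger study.

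**What to change.** 1. **Decision rule.** In sections 6 and 10, state that the primary heart-rate objective is met if the lower limit of the two-sided 95% confidence interval of the ICC between COBOX and the Contec CMS60D exceeds 0.6. In section 5, label 0.7 as the planning value.
2. **Reading, form and power.** State that the 15-second reading is primary and name the ICC form. Absolute agreement suits an objective of concordance, because a consistency ICC ignores a constant bias; the documents do not dictate this choice. Restate the power as about 74% at 226 usable patients, assuming negligible bias.
3. **Alternative.** If all three pairs are to be used, say so, and give a confidence interval and power that allow for two methods with repeated readings within a patient.

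The changes are wording and a recalculated power; they use data already collected. The cost is a less favourable stated power. Keeping 90% with one pair would take 348 usable patients (498 enrolled at 30% unusable), and would deliver it only if device bias is negligible, so stating the lower power is the proportionate course.
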